IWRS ⁽⁷⁾	X	X			X	X			X
Injection-site tolerance ⁽⁸⁾			X	X	X		X	X	X
Adverse events (AEs) ⁽⁹⁾					X				
Procedures/Therapeutic measures					X				

- (1) V1 can be performed on the same day as V2. MRI procedures, at V2 and V4, should be performed on the same day as IWRS connection
- (2) Physical examination should be performed by a physician: examination of general appearance, skin, neck (including thyroid), eyes, ears, nose, throat, lungs, heart, abdomen, back, lymph nodes, extremities, vascular and neurological. Information indicating the global assessment (normal or abnormal (specify)) of the physical examination should be recorded on source documentation.
- (3) Urine pregnancy test (if applicable) is to be done on site. At V2 and V4 results must be available prior to IWRS connection and administration of IMP. In case V1 and V2 are performed on the same day, only one pregnancy test is required.
- (4) At V2 and V4, creatinine and eGFR are to be evaluated locally, and results must be available prior to IWRS connection and administration of IMP. Starting at V3, change in local serum creatinine result should be checked as per ESUR guidelines (see [section 7.2.11](#)). The same local methods of serum creatinine dosage and eGFR calculation should be used throughout the trial for a same patient.
- (5) Clinical laboratory parameters will be analysed by the central laboratory: haematology and biochemistry (see [section 8.5](#))
- (6) Vital signs: BP: Blood Pressure (supine systolic and diastolic), PR: Pulse Rate
- (7) IWRS: connection should be done at each trial visit and in case of screening failure or premature discontinuation
- (8) Injection-site tolerance (pain, eruption, extravasation, inflammation, or other) is to be assessed during the injection, 60 ± 15 min and 1 day post injection.
- (9) AEs occurring during the time of the patient's participation in the trial, must be reported and followed, unless they meet the following definition: the events which that occur before the first IMP administration, and which are not serious and not related to the trial procedures may be recorded as medical history upon the investigator's judgement. Procedures/therapeutic measures for AE are also to be reported
- (10) All the assessments performed prior to the first MRI at V2 will be considered as baseline value
- (11) Some non-inclusion criteria must be checked again at V4 (see [section 4.2](#))

TRIAL DIAGRAM

Figure 1: Trial diagram

Guerbet

CONFIDENTIAL

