3.3 Trial Duration

3.3.1 *Duration of patient's participation*

Minimum trial duration for patients: 4 days, if V1 and V2 are done on the same day and the second MRI is done 2 days after the first one.

Maximum trial duration for patients: 23 days, if the screening period lasts 7 days and the second MRI is done 14 days after the first one.

The trial includes a maximum of 5 visits:

- One screening visit (V1) up to 7 days prior to inclusion (V1) could be done the same day as the randomization visit (V2) if all the inclusion/non-inclusion criteria are met).
- Two sequential imaging visits (V2 and V4, minimum interval 2 days and up to 14 days): each visit will consist of gadopiclenol injection or gadobutrol injection and MRI procedure.
- Two safety visits (V3 and V5): 1 day after each injection and MRI examination.

3.3.2 *End of trial*

The trial is considered as completed once all the images collected for all the patients have been reviewed by all the independent blinded readers.

The patient's participation is defined as the period from the screening visit (ICF signature) to the last trial visit.

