
The number and percentage of patients with at least one AESI with causal relationship to the IMP will be presented using the Safety Set by contrast agent group according to Primary SOC and PT.

11.3.8 ***Laboratory data***

Laboratory data analysis will be done using the Safety Set.

The statistical analysis will present results in standard international units and United States units. Original units will be only listed. Laboratory data will be analyzed quantitatively and qualitatively by contrast agent group. Qualitative analyses will be done via comparison of laboratory data to their reference ranges and according to their clinical significance. Quantitative analyses will be done by tabulating raw data and change from baseline. They will be displayed qualitatively as well by means of shift tables.

11.3.9 ***Other safety observations***

Other safety observations analysis will be done using the Safety Set.

Extent of exposure

Duration between ICF signature, IMP administrations and end of trial will be tabulated by contrast agent group.

Volume actually administered and, actual rate of administration, will be tabulated by contrast agent group.

Injection site tolerance

Number of patients experiencing pain, eruption, extravasation and inflammation at site injection will be tabulated by contrast agent group. Pain at injection site will be measured using the Numeric Pain intensity Scale (NPS) and NPS measurements for these patients will be tabulated by contrast agent group.

Vital signs

Vital signs will be analyzed quantitatively and qualitatively by contrast agent. Qualitative analyses will be done via comparison of vital signs data to their normal ranges (see [section 7.2.11](#)) and according to their clinically significant changes. Quantitative analyses will be done by tabulating raw data and change from baseline.

 CONFIDENTIAL	Protocol No. GDX-44-011 Version No. 3.0 (including amendment 2) June 30, 2020	Page 70 / 82
--	---	--------------

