Tabulations of frequencies for categorical data will include all possible categories and will display the number of observations in a category as well as the percentage (%) relative to the respective group. Percentages will be rounded to one decimal place. The category missing will be displayed only if there are actually missing values. Percentages will be calculated on the total of non-missing recorded categories.

For the safety evaluation, the **baseline value** will be defined as the last available value prior to the first administration of any investigational product.

Duration between two dates will be calculated as follow: date 2 – date 1 + 1

Time to event from date 1 will be calculated as follow: date of event – date 1.

SAS® version 9.4 will be used for all descriptive summaries and inferential analyses.

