### **5.7.3. Clinical laboratory evaluation**

All laboratory values recorded during the trial will be individually listed and flagged for values outside reference ranges if any (presented in CSR appendix 16.2.8). Parameters obtained centrally and those obtained locally will be presented together.

*Hematology data* include the following parameters (in SI and conventional units):

	SI units	Conventional units
Red Blood Cells (RBC) = Erythrocytes	10  /L	10  /µL
White Blood Cells (WBC) = Leukocytes	10  /L	10  /µL
Neutrophils	10  /L	10  /µL
Neutrophils/ Leukocytes	%	%
Eosinophils	10  /L	10  /µL
Eosinophils/ Leukocytes	%	%
Basophils	10  /L	10  /µL
Basophils/ Leukocytes	%	%
Lymphocytes	10  /L	10  /µL
Lymphocytes/ Leukocytes	%	%
Monocytes	10  /L	10  /µL
Monocytes/ Leukocytes	%	%
Platelet count	10  /L	10  /µL
Hemoglobin	g/L	g/dL
Hematocrit	v/v	%
Mean Corpuscular Volume (MCV)	fL	fL

*Biochemistry data* include the following parameters:

	SI units	Conventional units
Sodium	mmol/L	mEq/L
Potassium	mmol/L	mEq/L
Chloride	mmol/L	mEq/L
Blood Urea Nitrogen (BUN)	mmol/L	mg/dL
Urea*	mmol/L	mg/dL
Serum creatinine	umol/L	mg/dL
eGFR	mL/min/1.73m 	mL/min/1.73m 
Total protein	g/L	g/dL
Calcium	mmol/L	mg/dL
Phosphorus	mmol/L	mg/dL
Total bilirubin	umol/L	mg/dL
Indirect bilirubin	umol/L	mg/dL
Conjugated bilirubin	umol/L	mg/dL
Aspartate Amino Transferase (AST)	U/L	U/L
Alanine Amino Transferase (ALT)	U/L	U/L
Alkaline Phosphatase	U/L	U/L
Lactate DeHydrogenase (LDH)	U/L	U/L
Triglycerides	mmol/L	mg/dL
Cystatin C	mg/L	mg/L

\*Urea is derived from BUN. In SI unit, Urea=BUN, in conventional unit, Urea=BUN\*2.14

The baseline value for each laboratory parameter will be the last value measured before the first contrast agent administration (i.e. the assessment prior to 1st MRI).

In the tables and listings, the parameters will be ordered as follow:

- Hematology: Red Blood Cells (RBCs), hemoglobin, hematocrit, Mean red blood Cells Volume (MCV), White Blood Cells (WBCs)=leukocytes, neutrophils, neutrophils/leukocytes, lymphocytes, lymphocytes /leukocytes, monocytes, monocytes/leukocytes, eosinophils, eosinophils/leukocytes, basophils, basophils/leukocytes and platelet count.

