#### *Quantitative analysis*

Hematology and biochemistry parameters at visits 2, 3, 4 and 5 will be described as quantitative variables in both SI and conventional units as raw data and change from baseline. Numbers and percentages of patients with values out of range (lower than the lower limit or higher than the upper limit of normal range) will also be presented, except if values for normal ranges are unknown for a parameter

Same analyses will be repeated by body regions.

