#### *Qualitative analysis*

Shift tables presenting relative change from baseline in classes *versus* baseline in classes will be displayed for *serum creatinine*, *eGFR*, *BUN* and *cystatin C*.

Baseline data will be classified as follows (no baseline categories will be used for cystatin C):

SI units	Conventional units

 
• Serum creatinine (umol/L): 
 
○ < 60
 
○ <math>\geq</math> 60 and < 100
 
○ <math>\geq</math> 100
 
 
 
	
 
• Serum creatinine (mg/dL): 
 
• < 0.66
 
• <math>\geq</math> 0.66 and < 1.1
 
• <math>\geq</math> 1.1
 
 
 

 
• eGFR (mL/min/1.73m^2): 
 
○ < 60
 
○ <math>\geq</math> 60 and < 90
 
○ <math>\geq</math> 90
 
 
 
	
 
• eGFR (mL/min/1.73m^2): 
 
• < 60
 
• <math>\geq</math> 60 and < 90
 
• <math>\geq</math> 90
 
 
 

 
• BUN (mmol/L): 
 
○ < 2
 
○ <math>\geq</math> 2 and < 4
 
○ <math>\geq</math> 4 and < 6
 
○ <math>\geq</math> 6
 
 
 
	
 
• BUN (mg/dL): 
 
• < 5.6
 
• <math>\geq</math> 5.6 and < 11.2
 
• <math>\geq</math> 11.2 and < 16.8
 
• <math>\geq</math> 16.8
 
 
 

 
• Cystatin C (U/L): 
 
○ All
 
 
 
	
 
• Cystatin C (U/L): 
 
• All
 
 
 

Relative change from baseline will be calculated as follows:  $100^* \text{ (post injection measurement - baseline measurement) / baseline measurement}$ . Relative change from baseline will be classified as follows:

- $\leq -50\%$ .
- $> -50\%$  and  $\leq -25\%$ .
- $> -25\%$  and  $\leq -15\%$ .
- $> -15\%$  and  $< 0\%$ .
- $\geq 0\%$  and  $< 15\%$ .
- $\geq 15\%$  and  $< 25\%$ .
- $\geq 25\%$  and  $< 50\%$ .
- $\geq 50\%$ .

Numbers and percentages of patients in each class will be presented in both SI and conventional units.

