#### 6.1.3.4 *Laboratory data*

Table 14.3.3.11 Hematology Data - Raw data and Change from Baseline – SI Units – Safety Set

CONFIDENTIAL	STATISTICAL ANALYSIS PLAN PHASE III TRIAL GDX-44-011 VERSION NO. 2.0      DATED 25 JANUARY 2021	████████ Page 53 / 57
--------------	---	--------------------------

Table 14.3.3.2 Hematology Data - Raw data and Change from Baseline – Conventional US Units – Safety Set

Table 14.3.3.3 Biochemistry Data - Raw data and Change from Baseline – SI Units – Safety Set

Table 14.3.3.4 Biochemistry Data - Raw data and Change from Baseline – Conventional US Units – Safety Set

Table 14.3.3.5 Hematology Data - Raw data and Change from Baseline by Body Region – SI Units – Safety Set

Table 14.3.3.6 Hematology Data - Raw data and Change from Baseline by Body Region – Conventional US Units – Safety Set

Table 14.3.3.7 Biochemistry Data - Raw data and Change from Baseline by Body Region – SI Units – Safety Set

Table 14.3.3.8 Biochemistry Data - Raw data and Change from Baseline by Body Region – Conventional US Units – Safety Set

Table 14.3.3.9 Shift Table of Serum Creatinine, eGFR, BUN and Cystatin C between Baseline Measurement and Post-Injection Measurement – SI units – Safety Set

Table 14.3.3.10 Shift Table of Serum Creatinine, eGFR, BUN and Cystatin C between Baseline Measurement and Post-Injection Measurement – Conventional US units – Safety Set

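### Laboratory change under the second contrast agent is measured from before the first, so any remaining first-agent change enters its V5 change and shift class

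*SAP*

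**What the plan says.** The baseline rule is explicit and is the same throughout.

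- SAP 5.7.3: "The baseline value for each laboratory parameter will be the last value measured before the first contrast agent administration".
- SAP 3.1 gives the general safety rule: baseline "will be defined as the last available value prior to the first administration of any investigational product".
- SAP 2.3 schedules local and central samples before each injection, but takes as baseline only the one before the first.
- Protocol flow chart, footnote 10: "All the assessments performed prior to the first MRI at V2 will be considered as baseline value".

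Two sets of tables rest on this baseline. For the first, SAP 5.7.3 (quantitative analysis) states: "Hematology and biochemistry parameters at visits 2, 3, 4 and 5 will be described as quantitative variables", both as raw values and as change from baseline. The second is the shift tables for creatinine, eGFR, BUN and cystatin C. They classify relative change, whose numerator is "post injection measurement - baseline measurement", and are listed in SAP 6.1.3.4 as "Shift Table of Serum Creatinine, eGFR, BUN and Cystatin C between Baseline Measurement and Post-Injection Measurement". Neither place says which visits count as post-injection.

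Protocol 11.3.8 sets the presentation: "Laboratory data will be analyzed quantitatively and qualitatively by contrast agent group". SAP 3.1 likewise presents safety by the agent actually administered. The two imaging visits are separated by a "minimum interval 2 days and up to 14 days" (Protocol 3.3.1), and each is followed by a safety visit one day later.

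**The concern.** For the agent given at V4, the only later laboratory value is V5. Measured from V2, its change covers both injections, yet it appears under one agent. The V4 pre-injection sample would separate the two, but no section of the SAP derives V5 minus V4. Adverse events are treated differently: SAP 5.7.2 assigns an event starting between the injections to the first agent and a later one to the second.

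The safety profile of both agents is a stated objective (Protocol 2.2), and these are the planned by-agent change tables for the renal markers. Because the order is randomised 1:1, persistence does not favour one agent. It pulls the two agents' V5 results together, so a real difference would look smaller there.

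**Working it through.** The plan states no figure for laboratory change, so there is none to reproduce.

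**Inputs from the documents.** V4 falls 2 to 14 days after V2, and V3 and V5 fall one day after each injection, so V5 is 3 to 15 days after V2. Order is allocated 1:1. The shift-class limits used here are those of SAP 5.7.3. SAP section 4 reports 25 drop-outs among 245 enrolled; the target is 300.

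**Assumed, not in the documents.** The share r of the first agent's change still present at V4 and V5 (0 to 1, the same for both agents), additive effects, and the illustrative effect sizes and variability below.

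**Step 1, identity.** V5 - V2 = (V4 - V2) + (V5 - V4). The first bracket contains what remains of the first agent's change.

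**Step 2, contrast between agents.** Let a and b be the mean day-1 changes of agents A and B.

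- At V3: a - b, unaffected.
- At V5 against V2: A's column (sequence B-A) is a + rb and B's column (sequence A-B) is b + ra. The difference is (1 - r)(a - b).
- V3 and V5 pooled: the average of the two contrasts, (1 - r/2)(a - b).

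| r | V5 against V2 | V3 and V5 pooled |
|---|---|---|
| 0 | 100% | 100% |
| 0.25 | 75% | 87.5% |
| 0.5 | 50% | 75% |
| 1 | 0% | 50% |

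**Step 3, one patient.** Take creatinine 0.80, 1.00 and 1.20 mg/dL at V2, V4 and V5. Against V2 the second agent shows (1.20 - 0.80)/0.80 = +50%, the top shift class. Against V4 it shows (1.20 - 1.00)/1.00 = +20%, the class from 15% to below 25%.

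**Step 4, shift-class shares.** Suppose A raises creatinine by 10% and B by 0%, with independent log-normal error of SD s at each visit. In B's V5 column, the probability of a rise of at least 15% against V2 is 1 - Φ[ln(1.15/(1 + 0.10r)) / (s√2)]. Against V4 it is the same expression with r = 0.

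| s | Against V4 | Against V2, r = 0.25 | r = 0.5 | r = 1 |
|---|---|---|---|---|
| 0.03 | 0.05% | 0.3% | 1.6% | 14.7% |
| 0.05 | 2.4% | 5.2% | 9.9% | 26.5% |
| 0.08 | 10.8% | 15.5% | 21.1% | 34.7% |

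At s = 0.05, A's own V5 column also shows 26.5%, so at r = 1 the two agents cannot be told apart there.

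For patient numbers, 25/245 = 10.2% drop-out, 300 × 0.898 = 269, and 269/2 is about 135 per sequence. At s = 0.05 that is about 3 patients in B's column against V4, and 7, 13 and 36 against V2.

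**Step 5, the alternative baseline.** If a share r4 remains at V4 and r5 at V5, the contrast against V4 is (1 + r4 - r5)(a - b). It is exact when r4 = r5. With r4 = 0.5 and r5 = 0.4 it gives 110% of the true difference, where V2 gives 1 - 0.4 = 60%.

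**The case against.** A single untreated baseline is a legitimate, consistently stated choice. It shows each patient's cumulative departure from the unexposed state, which a V4 baseline does not. The size of the harm is wholly assumed: no section gives r, a 10% creatinine effect or the variability, and Protocol 5.3.1 treats the interval as a wash-out. All of this stands. It is a reason to keep the V2 view, but not to make it the only by-agent view.

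Much is also visible already. V3 gives an undiluted randomised comparison. V4 raw values and change from V2 are tabulated, and SAP 5.4.4 shows eGFR at V2 and V4 by agent. Out-of-range counts and clinically significant values do not use the baseline. Mean V5 minus V4 can be worked out from by-visit means, if these are split by agent and period, and per-patient values are listed. This limits the harm. What the planned tables cannot supply is the second agent's shift-class counts against its own pre-injection value.

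A V4 baseline has its own weakness. With values of 1.00, 0.80 and 1.20 at V2, V4 and V5, it gives +50% where V2 gives +20%. If the fall at V4 was noise, the larger figure is an artefact.

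A reader might also infer that the rule misclassifies post-contrast acute kidney injury. The documents do not support that. No planned table counts it or applies its absolute creatinine limit, and the shift classes are relative only. Creatinine is reviewed against the ESUR definition at V3, V4 and V5, the investigator reports significant changes as adverse events, and those are attributed by onset.

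**Conclusion.** The point holds as a weakness in the by-agent laboratory summaries. There is no contradiction between protocol and SAP. The V5 change and shift class shown under the second agent include any first-agent change still present, by arithmetic. The V5 contrast is then (1 - r) of the true difference, or (1 - r/2) pooled with V3, assuming additive effects and the same r for both agents. The actual size is unknown because r is undocumented, and it is nil at r = 0. The patient counts in the working are illustrations only.

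It would go too far to say that the plan hides a renal difference, since V3 would show a day-1 difference undiluted. The tables are descriptive and the efficacy conclusions are untouched. The change is still worth making, because the sample that separates the two agents is already scheduled.

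**What to change.** In SAP 5.7.3, for laboratory change and shift tables by contrast agent, define:

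- **Baseline:** the last value before injection of the agent concerned, that is V2 for the first agent and the V4 pre-injection value for the second.
- **Post-injection measurement:** V3 for the first agent and V5 for the second.
- **Retained view:** change from V2 at all visits, including V4, as the cumulative picture and as late follow-up of the first agent.

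Amend the baseline statements in SAP 2.3 (local and central laboratory parameters) and SAP 3.1 to allow this period-specific laboratory baseline; otherwise the SAP would contradict itself. Record it as a departure from footnote 10 of the protocol flow chart.

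No new samples are needed. The cost is a few re-derived or added table columns. Two statistical drawbacks should be accepted openly: slight overstatement of the contrast if the first agent's change is still reversing between V4 and V5 (110% in the example above), and sampling noise in V4 entering the second agent's change. Showing both views lets a reader judge each.

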#### *Quantitative analysis*

Hematology and biochemistry parameters at visits 2, 3, 4 and 5 will be described as quantitative variables in both SI and conventional units as raw data and change from baseline. Numbers and percentages of patients with values out of range (lower than the lower limit or higher than the upper limit of normal range) will also be presented, except if values for normal ranges are unknown for a parameter

Same analyses will be repeated by body regions.

#### *Qualitative analysis*

Shift tables presenting relative change from baseline in classes *versus* baseline in classes will be displayed for *serum creatinine*, *eGFR*, *BUN* and *cystatin C*.

Baseline data will be classified as follows (no baseline categories will be used for cystatin C):

SI units	Conventional units

 
• Serum creatinine (umol/L): 
 
○ < 60
 
○ <math>\geq</math> 60 and < 100
 
○ <math>\geq</math> 100
 
 
 
	
 
• Serum creatinine (mg/dL): 
 
• < 0.66
 
• <math>\geq</math> 0.66 and < 1.1
 
• <math>\geq</math> 1.1
 
 
 

 
• eGFR (mL/min/1.73m^2): 
 
○ < 60
 
○ <math>\geq</math> 60 and < 90
 
○ <math>\geq</math> 90
 
 
 
	
 
• eGFR (mL/min/1.73m^2): 
 
• < 60
 
• <math>\geq</math> 60 and < 90
 
• <math>\geq</math> 90
 
 
 

 
• BUN (mmol/L): 
 
○ < 2
 
○ <math>\geq</math> 2 and < 4
 
○ <math>\geq</math> 4 and < 6
 
○ <math>\geq</math> 6
 
 
 
	
 
• BUN (mg/dL): 
 
• < 5.6
 
• <math>\geq</math> 5.6 and < 11.2
 
• <math>\geq</math> 11.2 and < 16.8
 
• <math>\geq</math> 16.8
 
 
 

 
• Cystatin C (U/L): 
 
○ All
 
 
 
	
 
• Cystatin C (U/L): 
 
• All
 
 
 

Relative change from baseline will be calculated as follows:  $100^* \text{ (post injection measurement - baseline measurement) / baseline measurement}$ . Relative change from baseline will be classified as follows:

- $\leq -50\%$ .
- $> -50\%$  and  $\leq -25\%$ .
- $> -25\%$  and  $\leq -15\%$ .
- $> -15\%$  and  $< 0\%$ .
- $\geq 0\%$  and  $< 15\%$ .
- $\geq 15\%$  and  $< 25\%$ .
- $\geq 25\%$  and  $< 50\%$ .
- $\geq 50\%$ .

Numbers and percentages of patients in each class will be presented in both SI and conventional units.

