- Blood sample collection for serum creatinine dosage and verification that the local eGFR value is ≥ 30 mL/min/1.73 m²; The same local methods of serum creatinine dosage and eGFR calculation should be used throughout the trial for a same patient;
- Blood samples will be collected according to central laboratory manual;
- Assessment of local serum creatinine results as per ESUR guidelines (see [section 7.2.11](#))
- Assessment of AEs will be documented;

- IWRS connection will be done to obtain the IMP box number, to calculate the volume of IMP to be administered based on the body weight and to record the date of the visit;

Unenhanced and contrast-enhanced MRI examinations:

- Unenhanced and contrast-enhanced MRI will be performed according to the required sequences specified in [Section 8.2.2](#).

The appropriate dose/volume of gadopiclenol and gadobutrol will be administered by IV as a bolus using preferably a power injector in a peripheral vein of the antecubital region (recommended). IMP injection will be followed by a 0.9% saline flush injection.

The following information will be documented in the source document and reported on clinical eCRF pages: contrast agent injection date and time, location of injection site, actual volume administered (documentation of difference with theoretical volume), actual injection rate, overdose (if any), number of vials dispensed, number of IMP injected, injection method (power injector or manual), injection of saline flush (yes/no).

The start time of contrast injection will be recorded.

Procedures to be followed after MRI examination:

The patient will stay at the trial site for 60 ± 15 min after the MRI examination is completed and the following procedures will be performed:

- Use/change of concomitant treatments during the visit will be documented;
- Vital signs (systolic and diastolic BP and PR) will be obtained 60 minutes ± 15 minutes after the injection of contrast agent.
- Injection-site tolerance (pain, eruption, extravasation, inflammation, or other) will be assessed during the injection and 60 minutes ± 15 minutes after the injection of contrast agent; In case of pain, the patient will have to complete a Numeric Pain intensity scale to indicate the pain intensity. Any sign of local intolerance will be reported as AE in the corresponding clinical eCRF page.
- Assessment of AEs will be documented;
- Evaluation of the potential impact of IMP-enhanced MRI on patient treatment plan;

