## ○ Vital signs

Vital signs (supine systolic and diastolic blood pressures, pulse rate) will be measured and recorded according to the following schedules:

- prior to each contrast agent injection (baseline value is measurement prior to the first agent injection)
- At  $60 \pm 15$  minutes following each contrast agent injection
- One day after each contrast injection

- **Injection-site tolerance**

Injection-site tolerance (pain, eruption, extravasation, inflammation, or other) will be assessed over 1 day following each contrast injection (during the injection, 60 min ± 15 min post injection and the day after injection) and over a longer period if the investigator becomes aware of any related AE. In case of injection-site pain, the patient will be asked to specify the level of pain using a Numeric Pain intensity Scale from 0 (no pain) to 10 (maximal pain).

- **Local laboratory parameters**

Serum creatinine and eGFR will be collected according to the following schedules:

- prior to each contrast agent injection (baseline value is from samples collected prior to the first contrast agent injection)
- one day after each contrast agent injection

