### 3. STATISTICAL METHODS

#### 3.1. General considerations

With regards to the ICH topic E9 addendum, it has been decided to not use the wording estimand. Indeed, the protocol was drafted in 2018 when the addendum was not yet adopted by competent authorities (CA). Nevertheless, for this diagnostic cross-over study, all analyses and presentation asked by CA in this addendum were considered and put in place if needed. Hence, no strategy for dealing with intercurrent event is considered. However, sensitivity analyses are planned in order to assess the robustness of the primary analysis. As it is expected that very few patients dropped-out because of results of diagnostic of first period but rather for safety or technical reasons, no specific missing data handling is planned. However, a sensitivity analysis accounting for discontinued patient is planned (in the mixed models).

After the database lock, the statistical analysis will be performed by a Contract Research Organization ██████████ under the supervision of Guerbet biostatistician, on the basis of the present document.

A quality control of the statistical analysis will be performed by the CRO to ensure the reliability of the results prior to providing the results to Guerbet.

Some analyses will be presented by series (gadopiclenol-gadobutrol / gadobutrol- gadopiclenol), especially those about demographic and baseline characteristics. Some analyses will be presented by MR modality (pre /paired) and some by contrast agent group (gadopiclenol / gadobutrol), especially those in efficacy and safety. For the presentation by contrast agent group, efficacy analyses will be presented as randomized, that is to say presented by allocated contrast media whereas safety analyses will be presented by actually administered contrast media.

Tabulations of quantitative parameters will include the following summary statistics: Number of Patients / Mean / Standard Deviation / Minimum / Median / Maximum. If for a given parameter, the raw value has been collected with x decimal places, the mean, median and standard deviation will be rounded to x+1 decimal places, while the minimum and maximum values will be tabulated as reported with x decimal places.

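### Individual creatinine changes after the second agent are referenced only to the value before the first, and no table counts rises of 0.3 mg/dL: a cheap, optional addition

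*SAP*

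**What the plan says.** **Reference value.** SAP 5.7.3 states: "The baseline value for each laboratory parameter will be the last value measured before the first contrast agent administration". SAP 3.1 sets the same rule for safety in general. SAP 2.3 applies it to local creatinine and eGFR, which are sampled "prior to each contrast agent injection (baseline value is from samples collected prior to the first contrast agent injection". The SAP follows the protocol here; flow-chart note 10 reads: "All the assessments performed prior to the first MRI at V2 will be considered as baseline value".

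**Grouping.** Protocol 11.3.8: "Laboratory data will be analyzed quantitatively and qualitatively by contrast agent group". SAP 3.1 describes presenting "some by contrast agent group (gadopiclenol / gadobutrol), especially those in efficacy and safety", with safety shown by the agent actually given. The shift-table paragraph in SAP 5.7.3 does not repeat the grouping.

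**A second pre-dose value exists.** Before the second MRI, Protocol 8.1.4 requires "Blood sample collection for serum creatinine dosage and verification that the local eGFR value is" at least 30 mL/min/1.73 m².

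**Criterion.** Protocol 7.2.11 cites a definition of post-contrast acute kidney injury: a creatinine rise of at least 0.3 mg/dL, or to at least 1.5 times baseline, within 48 to 72 hours. Flow-chart note 4 says: "Starting at V3, change in local serum creatinine result should be checked as per ESUR guidelines". Protocol 8.1.3 to 8.1.5 repeat the check at V3, V4 and V5. Section 7.2.11 leaves it to the investigator to decide whether a change is clinically significant and so reported as an adverse event.

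**Tables.** For creatinine the SAP plans "Shift tables presenting relative change from baseline in classes" against baseline classes of below 0.66, 0.66 to below 1.1, and 1.1 mg/dL or more. The table list in SAP 6.1.3.4 contains no table of change from V4 and none that counts rises of 0.3 mg/dL.

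**The concern.** There are two separate gaps, both in a descriptive safety analysis.

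First, a patient's V5 change under the second agent is measured from before the first agent. It therefore combines any remaining first-agent effect, any drift over the 2 to 14 days between injections, and the second agent's own effect. For an individual patient the table cannot show which of these produced the rise, although the sample needed to separate them is taken.

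Second, sites are asked to check creatinine against a two-part criterion, but the report tabulates only one part in a recognisable form. Without a count of the absolute limb by agent, a reader who wants to know how many patients met the numeric criterion after each agent must work from listings.

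**Working it through.** **1. What V5 change contains.** For any patient, V5 − V2 = (V4 − V2) + (V5 − V4). Only the last term starts at the second injection. The values below are hypothetical, in mg/dL, and use the SAP's formula 100 × (post − baseline) / baseline:

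| V2 | V4 | V5 | Change from V2 | Change from V4 |
|---|---|---|---|---|
| 0.9 | 0.8 | 1.1 | +0.2 (+22.2%) | +0.3 (+37.5%) |
| 0.8 | 0.9 | 1.1 | +0.3 (+37.5%) | +0.2 (+22.2%) |
| 1.2 | 0.9 | 1.2 | 0.0 (0.0%) | +0.3 (+33.3%) |

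In the first two rows a shift of 0.1 mg/dL between V2 and V4 makes the two references disagree on the 0.3 mg/dL limb and on the percentage class. The rows show only that the references can differ. They do not show which is right.

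**2. What can be recovered at group level.** The quantitative part of SAP 5.7.3 summarises raw values and change from baseline at V2, V3, V4 and V5. When the same patients contribute,

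mean(V5 − V4) = mean(V5 − V2) − mean(V4 − V2).

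So the mean change after the second agent is not lost, provided V4 and V5 appear under the same agent. The spread of V5 − V4 and the number of patients above a threshold cannot be obtained this way.

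**3. The absolute limb against the percentage classes.** The 1.5-fold limb is 100 × (1.5 − 1) = +50%, so the top class shows it relative to V2. A rise of exactly 0.3 mg/dL from baseline b is 100 × 0.3 / b:

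| Baseline b (mg/dL) | Rise of 0.3 as % | SAP class |
|---|---|---|
| 0.6 | 50.0 | 50% or more |
| 0.66 | 45.5 | 25 to <50% |
| 1.0 | 30.0 | 25 to <50% |
| 1.1 | 27.3 | 25 to <50% |
| 1.2 | 25.0 | 25 to <50% |
| 1.5 | 20.0 | 15 to <25% |
| 2.0 | 15.0 | 15 to <25% |
| 2.1 | 14.3 | 0 to <15% |

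For V2 baselines below 1.1 mg/dL, every qualifying rise is above 27%, so the number of V2-referenced cases lies between the count at 50% or more and the count at 25% or more. In the open class of 1.1 or more the bound is looser. A change from 1.5 to 1.8 (+0.30, meets the limb) and one from 1.2 to 1.44 (+0.24, does not) are both +20% and fall in the same cell.

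**4. Timing.** V4 may fall on any of 14 − 2 + 1 = 13 whole-day intervals after V2, and V5 is one day later, so V5 is 3 to 15 days after the first injection. It is within 72 hours of both injections only at the 2-day interval (2 + 1 = 3 days), which is 1 of the 13. Scheduled post-dose sampling is at 1 day, so no table built on V3 and V5 can cover the full 48-to-72-hour window.

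**The case against.** The single baseline is deliberate and is stated consistently in both documents. The cited criterion refers to baseline, which flow-chart note 10 defines as V2, so on the trial's own terms 0.8/0.9/1.1 meets the 0.3 mg/dL limb and 0.9/0.8/1.1 does not. V4 is also a single measurement, open to the same variation and to residual first-agent effect. The numeric criterion was not made an endpoint: Protocol 7.2.11 defers to the investigator, and nephrogenic systemic fibrosis is the only event of special interest.

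Other planned output also helps. SAP 5.7.3 lists individual values and counts out-of-range ones. SAP 5.4.4 shows eGFR at V2 and V4 by agent. SAP 5.7.2 assigns adverse events to an agent by onset relative to the second injection. Non-inclusion criterion 13, rechecked at V4, names post-contrast kidney injury, so a patient recognised as having it should not receive the second agent. That limits large carry-over.

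Most of this stands. In particular, calling the first row of the illustration a missed case, or the second a false one, would presume that V4 is the correct reference, and the documents do not say so. A reader might also infer that the renal comparison is biased towards one agent or weakened by a fixed factor. The documents do not support that either. Order is randomised 1:1, the V3 comparison follows the first injection only, results are described by visit with no planned pooling of V3 and V5, and the size of any residual effect is not given.

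What the objection does not supply is a table that classifies individual patients against the value before the agent just given, or a count of the absolute limb. The adverse event tables and the table of clinically significant values include only changes the investigator judged significant.

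**Conclusion.** The point holds as a minor, optional improvement. The loss lies in patient-level classification after the second injection, and in the missing count of rises of 0.3 mg/dL, which is least recoverable at baselines of 1.1 mg/dL or more. First-period change, mean change by visit and adverse event attribution are not affected. It is not a conflict between protocol and SAP, since the SAP applies the protocol's baseline.

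The number of patients affected cannot be estimated: the documents give no creatinine distribution, between-visit variation or residual first-agent effect. If creatinine has returned to its V2 level by V4, the two references agree. The first part also assumes that the shift tables are shown by agent, as Protocol 11.3.8 and SAP 3.1 indicate.

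**What to change.** Keep the V2-based tables and the investigator-judged adverse event reporting unchanged. In SAP 5.7.3 and the table list, add:

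- One by-agent table of patients whose creatinine rises by at least 0.3 mg/dL, or to at least 1.5 times, from the last value before that agent's injection (V2 for the first agent, pre-dose V4 for the second), at the 1-day samples V3 and V5. Show the same count against the protocol-defined V2 baseline alongside.
- One listing of those patients, flagging V5 values that fall within 72 hours of both injections.

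Label both *creatinine criterion met at the sampled times*, so they are not read as full ascertainment of post-contrast kidney injury over 48 to 72 hours.

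The cost is one table and one listing from creatinine already collected at V2 to V5, with no new samples and no protocol change. The drawback is that V4 is an imperfect reference if a first-agent effect persists, which is why both counts should appear together.
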